8.12 Name and description of each Non-Investigational Medicinal Product (NIMP)

N/A

9 PHARMACOVIGILANCE

9.1 Definitions

Term	Definition
Adverse Event (AE)	Any untoward medical occurrence in a participant to whom a medicinal product has been administered, including occurrences which are not necessarily caused by or related to that product.
Adverse Reaction (AR)	An untoward and unintended response in a participant to an IMP which is related to any dose administered to that participant. The phrase "response to an IMP" means that a causal relationship between a trial medication and an AE is at least a reasonable possibility, i.e. the relationship cannot be ruled out. All cases judged by either the reporting medically qualified professional or the Sponsor as having a reasonable suspected causal relationship to the trial medication qualify as adverse reactions. It is important to note that this is entirely separate to the known side effects listed in the SmPC. It is specifically a temporal relationship between taking the drug, the half-life, and the time of the event or any valid alternative etiology that would explain the event.
Serious Adverse Event (SAE)	A serious adverse event is any untoward medical occurrence that: 
• results in death• is life-threatening• requires inpatient hospitalisation or prolongation of existing hospitalisation• results in persistent or significant disability/incapacity• consists of a congenital anomaly or birth defect Other 'important medical events' may also be considered serious if they jeopardise the participant or require an intervention to prevent one of the above consequences.

	
NOTE: The term "life-threatening" in the definition of "serious" refers to an event in which the participant was at risk of death at the time of the event; it does not refer to an event which hypothetically might have caused death if it were more severe.

Serious Adverse Reaction (SAR)	An adverse event that is both serious and, in the opinion of the reporting Investigator, believed with reasonable probability to be due to one of the trial treatments, based on the information provided.
Suspected Unexpected Serious Adverse Reaction (SUSAR)	A serious adverse reaction, the nature and severity of which is not consistent with the information about the medicinal product in question set out in the reference safety information:

9.2 Operational definitions for (S)AEs

As the IMP has a well-known and well established safety profile, new or unreported AEs and ARs are not expected in such a small trial. All AEs and ARs will be recorded. Acute exacerbations are expected to occur in COPD patients and therefore will not be recorded as (S)AEs or ((S)ARs). Breaking the blind will only take place where information about the participant's trial treatment is clearly necessary for the appropriate medical management of the participant

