9.3 Recording and reporting of SAEs, SARs AND SUSARs

All SAEs / SAEs occurring from the time of written informed consent until 30 days post cessation of trial treatment must be recorded on the AE Form and emailed to the Sponsor ([contact]) within 24 hours of the research staff becoming aware of the event.

For each SAEs the following information will be collected:

- Full details in medical terms and case description
- Event duration (start and end dates, if applicable)
- Action taken
- Outcome
- Seriousness criteria
- Causality (i.e. relatedness to trial drug / investigation), in the opinion of the investigator
- Whether the event would be considered anticipated.

Any change of condition or other follow-up information should be emailed to the Sponsor as soon as it is available or at least within 24 hours of the information becoming available. Events will be followed up until the event has resolved or a final outcome has been reached.

All ARs/SARs/SUSARs occurring from the time of start of trial treatment until 30 days post cessation of trial treatment must be recorded on the AE Form and emailed to the Sponsor within 24 hours of the research staff becoming aware of the event.

For each AR/SAR/SUSAR the following information will be collected:

- Full details in medical terms and case description
- Event duration (start and end dates, if applicable)
- Action taken
- Outcome
- Seriousness criteria
- Causality (i.e. relatedness to trial drug / investigation), in the opinion of the investigator
- Whether the event would be considered anticipated.

Any change of condition or other follow-up information will be emailed to the Sponsor as soon as it is available or at least within 24 hours of the information becoming available. Events will be followed up until the event has resolved or a final outcome has been reached.

All SAEs assigned by the PI or delegate (or following central review) as both suspected to be related to IMP treatment and unexpected will be classified as SUSARs and will be subject to expedited reporting to the Medicines and Healthcare Products Regulatory Agency (MHRA). The CI/delegated team will inform the Sponsor, MHRA, the REC and Marketing Authorisation Holder (if not the sponsor) of SUSARs within the required expedited reporting timescales: fatal and life-threatening within 7 days of notification and non-life threatening within 15 days.

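### Section 9.2 exempts every acute exacerbation from adverse-reaction recording, so a serious exacerbation suspected to be drug-related has no required route to causality assessment, sponsor report or SUSAR review

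*Combined protocol and SAP*

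**What the plan says.** Section 9.2 (Operational definitions for (S)AEs) first sets a general rule, "All AEs and ARs will be recorded", and then an exemption: "Acute exacerbations are expected to occur in COPD patients and therefore will not be recorded as (S)AEs or ((S)ARs". The bracketed letters take in serious events as well as events suspected to be caused by the drug.

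The surrounding sections contain no such exemption:

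- **9.1, seriousness.** An event is serious by its outcome. Besides death and threat to life, the list includes an event that "requires inpatient hospitalisation or prolongation of existing hospitalisation".
- **9.1, adverse reaction.** The test is suspected causality, and either of two parties may apply it: "either the reporting medically qualified professional or the Sponsor as having a reasonable suspected causal relationship to the trial medication qualify as adverse reactions".
- **9.3, SAEs.** All SAEs "occurring from the time of written informed consent until 30 days post cessation of trial treatment must be recorded on the AE Form" and go to the sponsor within 24 hours. All ARs, SARs and SUSARs carry the same 24-hour duty from the start of treatment. The items to be collected include "Causality (i.e. relatedness to trial drug / investigation), in the opinion of the investigator".
- **9.3, SUSARs.** SAEs assessed "as both suspected to be related to IMP treatment and unexpected will be classified as SUSARs", with expedited reporting: "fatal and life-threatening within 7 days of notification and non-life threatening within 15 days".
- **9.4.** Item 8 has the CI ensure that all SAEs are recorded and reported within 24 hours. Items 3 and 4 judge whether an event was anticipated against the Reference Safety Information.
- **9.10.** That reference is section 4.8 of the metformin SmPC.

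Exacerbations are also a secondary endpoint, as a count (3.5), and are asked about at monthly visits (7.7).

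**The concern.** Being common in the disease is a reason to spare sites expedited paperwork for events that nobody attributes to the drug. It does not show that a particular event was not caused by the drug. Section 9.2 uses the first idea to settle the second: once an event is labelled an exacerbation, it leaves the safety system whatever its severity and whatever the investigator suspects.

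At stake is individual-case safety oversight, not the primary sputum glucose comparison. The affected events are those where a case-by-case judgement is most useful: an exacerbation that leads to admission, threatens life or is fatal, in a participant whose clinician suspects the study drug. Staff who follow 9.2 and staff who follow 9.3 would handle the same event differently, and nothing in the protocol says which section prevails.

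**Working it through.** No arithmetic is needed for the main point. The check is to trace each kind of exacerbation through 9.1, 9.3 and 9.2.

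| Exacerbation | Under 9.1 and 9.3 alone | Under 9.2 | Can 9.2 be defended? |
|---|---|---|---|
| Non-serious, not suspected related | AE, recorded | Not recorded as AE | Yes; it is still counted as an outcome (3.5, 7.7) |
| Serious, judged unrelated | SAE, sponsor within 24 hours | Not recorded as SAE | As to fast reporting, yes; as to recording, weakly, since no one is required to make the judgement of unrelatedness |
| Non-serious, suspected related | AR, sponsor within 24 hours | Not recorded as AR | No |
| Serious, suspected related | SAR, sponsor within 24 hours; SUSAR if unexpected | Not recorded as SAE or SAR | No |

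**Step 1: what is lost.** For each SAE, AR or SAR, 9.3 asks for seven items: case description, duration, action taken, outcome, seriousness criteria, causality, and whether the event was anticipated. Section 9.2 removes that requirement for every exacerbation. Sections 3.5 and 7.7 ask for a number and for data on exacerbations; they name none of the seven.

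**Step 2: the SUSAR step.** Section 9.3 selects SUSARs from among SAEs. An event that 9.2 keeps from being recorded as an SAE does not enter that selection, so the 7-day and 15-day clocks have nothing to start them.

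**Step 3: the expectedness test.** Section 9.2 reasons from what is expected in COPD patients. Sections 9.4 and 9.10 judge expectedness against SmPC section 4.8. These are different tests, and only the second bears on whether a suspected reaction is a SUSAR. The SmPC text is not in the documents, so how a given case would be classified cannot be settled here. The point is that the classification would never be made.

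**Step 4: fatal exacerbations.** Other deaths are SAEs under 9.1 and reportable under 9.3. A fatal exacerbation, exempt under 9.2, would reach the sponsor only through 9.5, which is confined to deaths that come earlier than expected. That term is not defined.

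**Step 5: the link to withdrawal.** Criterion 2 in 7.10 withdraws any participant with an SAE. If serious exacerbations became SAEs with no other change, each one would force withdrawal, and participants would leave for having an outcome under study. Section 10.7 restricts the analysis to participants with the required drug exposure, so they would probably also leave the analysis. A correction to 9.2 therefore needs a matching edit in 7.10.

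**The case against.** The best defence is that 9.2 is headed as operational definitions. Its job is to say how the general terms of 9.1 apply in this trial, so the references to all SAEs in 9.3 and 9.4 would mean SAEs as narrowed by 9.2. There is a practical reason for such a rule: exacerbations are an endpoint, and 7.10 would otherwise withdraw participants for having a serious one. This stands for unrelated exacerbations. A reader might infer that 9.2 flatly contradicts 9.1, 9.3 and 9.4 for every serious exacerbation; the documents do not support that, because a deliberate exemption is a fair reading for events not attributed to the drug. The defence does not reach suspected reactions. Such an event is by definition not being put down to background disease alone, and neither the heading nor the endpoint role explains why it should go unrecorded.

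A reader might also infer that the sponsor is shut out of judging causality altogether. That goes too far. Section 11.3 gives sponsor representatives direct access to data, and section 12 provides for risk-based monitoring. What is lost is prompt notification and a required assessment; neither access nor monitoring supplies those.

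Other safeguards remain: the CI's ongoing risk/benefit review (9.4), emergency unblinding (7.5) and urgent safety measures (9.8). A separately diagnosed event such as lactic acidosis is not exempt. The CRF is not in the documents and may record seriousness or causality for exacerbations. These limit the harm, but none of them is a stated duty to assess and report the individual event.

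**Conclusion.** The concern holds for suspected drug-related exacerbations, and most clearly for serious ones. For these, 9.2 as written removes the required causality assessment, the 24-hour sponsor report and entry to SUSAR review, against 9.1, 9.3 and 9.10. For unrelated exacerbations, exemption from fast reporting is a defensible design choice. The remaining weakness there is that relatedness need not be assessed or recorded before the exemption applies.

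The number of affected events cannot be derived, because the documents give no exacerbation or hospitalisation rate. A reader might infer from section 1, which ties exacerbations to mortality and frequent hospitalisation, that many would be serious. That statement describes COPD in general. Entrants here have been free of infection for at least 8 weeks (6.1), and respiratory failure is an exclusion (6.2).

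The conclusion assumes that staff apply 9.2 literally and that no document outside those reviewed restores the missing steps. It does not depend on any event rate, and the sponsor should correct the wording.

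**What to change.** **9.2.** Limit the exemption to exacerbations that are non-serious and not suspected to be related to the IMP. Require every serious exacerbation to be assessed for causality and recorded. Report any suspected-related exacerbation under 9.3. Clearly unrelated serious ones may be exempted from 24-hour reporting, but not from recording. Refer to this rule in 9.3 and 9.4 item 8 so that the sections agree.

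**7.10, criterion 2.** State that an unrelated serious exacerbation does not by itself force withdrawal. Criterion 3 still withdraws a participant when an unrelated event requires it.

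**9.5.** Remove the restriction to deaths that come earlier than expected, so that a fatal exacerbation is always notified.

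**Cost.** An amendment through 13.10, a few more SAE forms, and a slightly narrower withdrawal rule. No visits or samples are added.

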9.3 Recording and reporting of SAEs, SARs AND SUSARs

All SAEs / SAEs occurring from the time of written informed consent until 30 days post cessation of trial treatment must be recorded on the AE Form and emailed to the Sponsor ([contact]) within 24 hours of the research staff becoming aware of the event.

For each SAEs the following information will be collected:

- Full details in medical terms and case description
- Event duration (start and end dates, if applicable)
- Action taken
- Outcome
- Seriousness criteria
- Causality (i.e. relatedness to trial drug / investigation), in the opinion of the investigator
- Whether the event would be considered anticipated.

Any change of condition or other follow-up information should be emailed to the Sponsor as soon as it is available or at least within 24 hours of the information becoming available. Events will be followed up until the event has resolved or a final outcome has been reached.

All ARs/SARs/SUSARs occurring from the time of start of trial treatment until 30 days post cessation of trial treatment must be recorded on the AE Form and emailed to the Sponsor within 24 hours of the research staff becoming aware of the event.

For each AR/SAR/SUSAR the following information will be collected:

- Full details in medical terms and case description
- Event duration (start and end dates, if applicable)
- Action taken
- Outcome
- Seriousness criteria
- Causality (i.e. relatedness to trial drug / investigation), in the opinion of the investigator
- Whether the event would be considered anticipated.

Any change of condition or other follow-up information will be emailed to the Sponsor as soon as it is available or at least within 24 hours of the information becoming available. Events will be followed up until the event has resolved or a final outcome has been reached.

All SAEs assigned by the PI or delegate (or following central review) as both suspected to be related to IMP treatment and unexpected will be classified as SUSARs and will be subject to expedited reporting to the Medicines and Healthcare Products Regulatory Agency (MHRA). The CI/delegated team will inform the Sponsor, MHRA, the REC and Marketing Authorisation Holder (if not the sponsor) of SUSARs within the required expedited reporting timescales: fatal and life-threatening within 7 days of notification and non-life threatening within 15 days.

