ISRCTN	International Standard Randomised Controlled Trials Number
MA	Marketing Authorisation

MHRA	Medicines and Healthcare products Regulatory Agency
MS	Member State
NHS R&D	National Health Service Research & Development
NIMP	Non-Investigational Medicinal Product
PI	Principal Investigator
PIC	Participant Identification Centre
PIS	Participant Information Sheet
QA	Quality Assurance
QC	Quality Control
QP	Qualified Person
RCT	Randomised Control Trial
REC	Research Ethics Committee
SAE	Serious Adverse Event
SAM	Synthetic Absorption Matrix
SAR	Serious Adverse Reaction
SDV	Source Data Verification
SOP	Standard Operating Procedure
SmPC	Summary of Product Characteristics
SSI	Site Specific Information
SUSAR	Suspected Unexpected Serious Adverse Reaction
TMF	Trial Master File
TMG	Trial Management Group
TSC	Trial Steering Committee

iii. TRIAL SUMMARY

Trial Title	A pilot, randomised, double-blind, placebo-controlled, cross-over study of metformin to reduce airway glucose in chronic obstructive pulmonary disease (COPD)	
Internal ref. no. (or short title)	A pilot study of metformin to reduce airway glucose in COPD	
Clinical Phase	Exploratory Phase II pilot study	
Trial Design	Randomised, double-blind, placebo-controlled, cross-over	
Trial Participants	Chronic obstructive pulmonary disease (COPD) patients	
Planned Sample Size	40 subjects	
Treatment duration	3 months one study arm, 2 weeks wash out, 3 months in other study arm	
Follow up duration	6.5 months	
Planned Trial Period	24 months	
	Objectives	Outcome Measures
Primary	Effect of metformin on airway glucose	Sputum glucose after 3 months treatment with metformin
Secondary	Effects of metformin on: 1. Glucose levels in the nose 2. Bacterial infection 3. Inflammation in the lung 4. COPD exacerbations 5. Quality of life and symptoms 6. Lung function	1. Glucose levels in nasal SAM strips 2. Bacterial load in sputum 3. Inflammatory markers in sputum 4. Number of COPD exacerbations 5. Quality of life and symptom scores 6. Spirometry
Investigational Medicinal Product(s)	Metformin	
Formulation, Dose, Route of Administration	1000mg bd, po	

iv. FUNDING AND SUPPORT IN KIND

FUNDER(S) (Names and contact details of ALL organisations providing funding and/or support in kind for this trial)	FINANCIAL AND NON FINANCIAL SUPPORT GIVEN
NIHR Imperial Biomedical Research Centre (BRC)	£ 173,511

v. ROLE OF TRIAL SPONSOR AND FUNDER

[figure not shown]

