7.12 End of trial

The end of the trial will be the date of the last visit of the last patient undergoing the trial.

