9.4 Responsibilities

Chief Investigator (CI):

1. Checking for AEs and ARs when participants attend for treatment / follow-up.
2. Clinical oversight of the safety of patients participating in the trial, including an ongoing review of the risk / benefit.
3. Using medical judgement in assigning the SAEs seriousness, causality and whether the event was anticipated (in line with the Reference Safety Information) where it has not been possible to obtain local medical assessment.
4. Using medical judgement in assigning whether an event/reaction was anticipated or expectedness in line with the Reference Safety Information.
5. Immediate review of all SUSARs.
6. Review of specific SAEs and SARs in accordance with the trial risk assessment and protocol as detailed in the Trial Monitoring Plan.

7. Assigning Medical Dictionary for Regulatory Activities (MedDRA) or Body System coding to all SAEs and SARs.
8. Ensuring that all SAEs are recorded and reported to the sponsor within 24 hours of becoming aware of the event and provide further follow-up information as soon as available.
9. Ensuring that AEs and ARs are recorded and reported to the sponsor in line with the requirements of the protocol.
10. Expedited reporting of SUSARs to the MHRA and REC within required timelines.
11. Notifying Investigators of SUSARs that occur within the trial.
12. Checking for and notifying PIs of updates to the Reference Safety Information for the trial.

Sponsor:

1. Central data collection and verification of AEs, ARs, SAEs, SARs and SUSARs according to the trial protocol onto a database.
2. The unblinding of a participant for the purpose of expedited SUSAR reporting.

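### The 30-day safety window in section 9.3 runs past the last scheduled visit and the end of trial, and no contact is planned to collect events in it

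*Combined protocol and SAP*

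**What the plan says.** Section 9.3 sets two windows with the same end point. Serious adverse events occurring from written consent "until 30 days post cessation of trial treatment must be recorded on the AE Form". For reactions the rule is: "All ARs/SARs/SUSARs occurring from the time of start of trial treatment until 30 days post cessation of trial treatment must be recorded". Both are to reach the sponsor "within 24 hours of the research staff becoming aware of the event".

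For other adverse events, section 9.2 says only "All AEs and ARs will be recorded", with no end date. Section 9.4 gives the means of finding events as a duty of the chief investigator: "Checking for AEs and ARs when participants attend for treatment / follow-up".

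The trial summary gives the treatment duration as "3 months one study arm, 2 weeks wash out, 3 months in other study arm" and the follow-up as 6.5 months. The last column of the Appendix 2 schedule is the three-month visit of Arm 2. Section 7.8 marks long-term follow-up as not applicable. Section 7.12 states: "The end of the trial will be the date of the last visit of the last patient undergoing the trial". Section 7.4 mentions a close-out visit before unblinding and creation of the locked dataset, but gives it no date, does not say whether participants attend it, and does not place it in the schedule.

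**The concern.** The protocol defines reportable events by when they occur, and the window continues for 30 days after the last dose. The only described way of finding events is to ask participants when they attend, and no attendance is scheduled in those 30 days. The same holds for participants who leave early: section 7.10 lists reasons for withdrawal but describes no later contact.

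What is at stake is the completeness of the safety data after treatment stops. A non-serious reaction, or an admission to another hospital, can go unrecorded without anyone departing from the protocol. In addition, the trial can formally end, and the dataset be locked, while the last participants are still inside the reporting window. The primary endpoint, sputum glucose at three months, is not affected.

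**Working it through.** **Inputs.** Two treatment periods of 3 months and a 2-week washout (trial summary); follow-up 6.5 months and trial period 24 months (trial summary); 30-day window (section 9.3); 40 participants recruited over 12 months at 3 to 4 a month (section 10.2); 30 participants required, with 40 recruited to allow for withdrawals (section 10.1); one month's supply per dispensing (section 8.4), last dispensed at Arm 2 month 2 (Appendix 2); simple randomisation (section 7.3).

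**1. The plan's own follow-up figure.** 3 + 0.5 + 3 = 6.5 months, which reproduces the trial summary. In days, 2 x 91.3 + 14 = 196.6. Follow-up therefore ends with the second period: 0 days are scheduled after it, against 30 required.

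**2. When treatment ends.** The last one-month supply is handed out at Arm 2 month 2, so the last dose falls at about the Arm 2 month-3 visit. From first dose to the close of the window is 196.6 + 30 = 226.6 days; the part with no planned contact is 30/226.6 = 13%.

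**3. After the first period.** The 30 days consist of 14 days of washout and the first 16 days of period 2. The Arm 2 baseline visit falls at about day 14 and the Arm 2 month-1 visit at about day 14 + 30.4 = 44. Section 7.7 has adverse events collected at the monthly visits, with the same protocol followed in period 2, and section 9.4 has them checked whenever participants attend. This window is covered, partly by recall at the month-1 visit.

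**4. Size of the gap.** Each treated participant has one final cessation, so the upper bound is 40 x 30/365 = 3.3 person-years. If only 30 complete, the completers' share is 30 x 30/365 = 2.5. About half of the 40 take metformin second, so about 20 x 30/365 = 1.6 person-years follow metformin. For scale, planned time on study treatment, metformin and placebo together, is 40 x 6/12 = 20 person-years.

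**5. End of trial.** At 3 to 4 recruits a month, about 3 to 4 participants have their final visit in the last 30 days of the trial. Their windows are still open at the end defined in section 7.12, by up to 30 days for the very last participant. The other completers' windows have closed by then.

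**6. Room for a later contact.** The last scheduled visit falls at about 12 + 6.5 = 18.5 months. Adding one month gives 19.5, within the 24 planned.

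**The case against.** The best defence is that section 9.3 starts the reporting clock when staff become aware and does not require anyone to go looking. Awareness is possible after the last visit: participants come from the clinical service in which the principal investigator works (sections 7.1 and 7.1.1), section 9.9 keeps SUSARs reportable however late they arise, and section 9.3 follows known events to resolution. This stands as far as it goes. A reader might infer that the window cannot be met, or that events in it are necessarily missed; the documents do not support that. But these provisions govern what happens once an event is known and add no planned means of learning of it.

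The close-out visit in section 7.4 might be offered as the missing contact. It is untimed and not described as a participant visit, so it does not settle the matter.

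Three further readings go too far:

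- That the gap follows both periods. The Appendix 2 table, as it reaches us, shows no adverse-event marks at Arm 2 baseline and month 1, but sections 7.7 and 9.4 have events collected at attended visits, and the blanks may come from conversion of the table.
- That the window covers all adverse events. As written it covers SAEs and ARs/SARs/SUSARs. The sentence on serious events names SAEs twice, and one may have been meant as AEs, but that is not what it says.
- That 3.3 person-years is all drug-related exposure. It is an upper bound, and about half of it follows placebo.

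Finally, section 2.1 reports that the gastrointestinal effects are most frequent when therapy is started, which limits the likely yield of late follow-up.

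**Conclusion.** The mismatch is real and modest. For SAEs and ARs/SARs/SUSARs in the 30 days after final cessation, the protocol describes no active ascertainment, either for completers or for participants who withdraw early. Capture is passive and probably incomplete. The time concerned is at most 3.3 person-years, about 1.6 of it after metformin, and the formal end of trial can precede closure of the window for about 3 to 4 participants.

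This assumes that treatment stops at about the Arm 2 month-3 visit, that recruitment runs evenly at the planned rate, that allocation to the two sequences is about equal, and that the close-out visit is not a timed participant contact. Since either treatment may come second, the gap falls on metformin and placebo about equally in expectation. It is a loss of safety information more than a bias between treatments.

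**What to change.** Reconcile section 9.3 with sections 7.8 and 7.12, the follow-up duration in the trial summary and the Appendix 2 schedule:

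- Add one brief safety contact, for example by telephone, at the end of the 30-day window after each participant's last dose. Include those who withdraw early, as far as their consent allows.
- Define the end of trial as the last such contact, and change the stated follow-up from 6.5 to about 7.5 months.
- State in section 7.4 whether the close-out visit is this contact. If it is not, say what it is, and place database lock after the last safety contact.

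If passive reporting after the last visit is what the sponsor intends, section 9.3 should say so, so that the safety results can be read accordingly.

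This is a cheap improvement. It costs about 40 short calls and one more month, taking the last contact from about month 18.5 to about month 19.5 of the 24 planned. It adds no clinic visit and leaves the primary analysis unchanged.
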